10. STATISTICAL METHODOLOGY

10.1 General

Data listings and summary statistics and statistical analyses will be performed for subjects included in the relevant analysis populations (All Subjects/ITT/Safety/PK).

For continuous data, summary statistics will include number of observations (n), the arithmetic mean, arithmetic standard deviation (SD), median, minimum (Min), and maximum (Max); for log-normal data (eg, the PK parameters: AUCs and C_{max}) the geometric mean and geometric coefficient of variation expressed as a percentage (CV%) will also be presented. For categorical data, frequency counts and percentages will be presented. For the calculation of summary statistics and statistical analysis, unrounded data will be used.

Baseline is defined as the last value for each assessment prior to the subject's first dose, including unscheduled values. Mean change from baseline is the mean of all individual subjects' change from baseline values. Each individual change from baseline will be calculated by subtracting the individual

subject's baseline value from the value at the timepoint. The individual subject's change from baseline values will be used to calculate the mean change from baseline using appropriate SAS[®] procedures such as Proc Univariate.

Missing values will not be imputed.

Data analysis will be performed using SAS[®] Version 9.3.

Analysis Data Model (ADaM) datasets will be prepared using Clinical Data Interchange Standards Consortium (CDISC) Analysis Data Model Version 2.1, and CDISC ADaM Implementation Guide Version 1.1. Pinnacle 21 Version 2.1.0 or higher will be utilized to ensure compliance with CDISC standards.

10.1.1 Unscheduled Readings

Unscheduled readings are defined as readings collected >15 minutes from the actual time of the original reading. Where results are taken in triplicate, the original reading is defined as the first reading of the triplicate. Unscheduled readings are labelled as 'Unscheduled' in the listings.

10.2 Protocol Deviations

Protocol deviations will be reviewed for their impact on the study data, and will be listed and tabulated.

10.3 Demographics and Subject Disposition

The demographic variables age, sex, race, ethnicity, body weight, height and body mass index will be summarized and listed. Subject disposition will be summarized and listed.

10.4 Medical History, and Previous and Concomitant Medications

Subjects' medical history will be listed. Previous and concomitant medications will also be listed. Prior medication includes medication taken and ended before the initiation of study drug. Concomitant medication includes medication started after the first dose of study, or taken prior to the first dose of study drug and that is continued during the study.

10.5 Pharmacokinetic Assessment

10.5.1 Pharmacokinetic Analysis

Where possible, the following PK parameters will be determined from UV-4 plasma concentrations on Day 1 and Day 7 and using non-compartmental methods³ performed in Phoenix WinNonlin (Certara USA, Inc., Version 6.4 or higher):

Parameter	Definition
C _{max}	Observed maximum plasma concentration
t _{max}	Time to reach maximum plasma concentration
AUC _(0-last)	Area under the concentration-time curve from time zero to time of last quantifiable concentration after the final dose on Day 7, calculated using the linear trapezoidal rule for increasing concentrations and the logarithmic rule for decreasing concentrations

$AUC_{(0-8)}$	Area under the concentration-time curve from time zero to 8 hours after first daily dose on Day 1 and after the final dose on Day 7, calculated using the linear trapezoidal rule for increasing concentrations and the logarithmic rule for decreasing concentrations
$AUC_{(0-24)}$	Total daily exposure at steady state, calculated as $AUC_{(0-8h)} \times 3$ (Day 7 last dose only)
CL/F	Apparent systemic clearance at steady state (Day 7 only), calculated as dose divided by $AUC_{(0-8)}$
V_z/F	Apparent volume of distribution during the terminal phase, calculated as $CL/F / \lambda_z$ after multiple doses (Day 7 only)
$t_{1/2}$	Apparent terminal half-life (Day 7 only), calculated as $\ln(2)/\lambda_z$
AR	Accumulation ratio, calculated as $AUC_{(0-8)}$ after last dose/ $AUC_{(0-8)}$ after first dose

Additional PK parameters may be determined where appropriate.

Pharmacokinetic analysis will be carried out using actual sampling times.

Concentrations for PK analyses will be used as supplied by the analytical laboratory. The units of concentration and resulting PK parameters, with amount or concentration in the unit, will be presented as they are received from the analytical laboratory.

If multiple peaks occur, the highest postdose concentration will be reported as C_{max} . In the case that multiple peaks are of equal magnitude, the earliest t_{max} will be reported.

10.5.2 Criteria for Handling Concentrations Below the Limit of Quantification in Pharmacokinetic Analysis

- Concentration values that are below the level of quantification (BLQ) will be set to zero, with defined exceptions as follows;
 - Any embedded BLQ value (BLQ value occurring between 2 quantifiable concentrations) and BLQ values following the last quantifiable concentration in a profile will be set to missing for the purposes of PK analysis.
 - If there are late positive concentration values following 2 BLQ concentration values in the apparent terminal phase, these values will be evaluated. If these values are considered to be anomalous, they will be set to missing.
 - If an entire concentration-time profile is BLQ, the profile will be excluded from the PK analysis.
 - If a predose concentration is missing prior to the first daily dose on Day 1, these values will be set to zero.

10.5.3 Criteria for the Calculation of an Apparent Terminal Elimination Half-life

10.5.3.1 Number of Data Points

- At least 3 data points will be included in the regression analysis and, preferably, should not include C_{max} . C_{max} may be included if needed to provide 3 data points.

10.5.3.2 Goodness of Fit

- When assessing terminal elimination phases, the adjusted coefficient of determination of exponential fit (R^2 adjusted) will be used as a measure of the goodness of fit of the data points to the determined line.
- An elimination half-life will only be calculated if the R^2 adjusted value of the regression line is greater than or equal to 0.7.

10.5.3.3 Period of Estimation

- The $t_{1/2}$ will be estimated over a time period of at least two half-lives, where possible.
- Where a $t_{1/2}$ is estimated over a time period of less than two half-lives, it will be flagged in the data listings at the discretion of the Pharmacokineticist, and the robustness of the value will be discussed in the CSR.

10.5.4 Calculation of AUC

- The minimum requirement for the calculation of AUC will be the inclusion of at least 3 consecutive plasma concentrations above the lower limit of quantification (LLOQ), with at least one of these concentrations following C_{max} .

10.5.5 Anomalous Values

- If a value is considered to be anomalous by being inconsistent with the expected PK profile, it may be appropriate to exclude this point from the PK analysis. However, the exclusion of data must have strong justification and will be documented in the raw data and CSR.
- Embedded BLQ values may be considered anomalous depending on the route of administration and the characteristics of the drug.
- Positive predose value(s) greater than 5% of C_{max} on Day 1 may be excluded from the summary statistics of PK tables and statistical analysis at the discretion of the Pharmacokineticist.

10.6 Presentation of Pharmacokinetic Data

10.6.1 Presentation of Pharmacokinetic Plasma Drug Concentration Data

- The following rules will be applied if there are values that are BLQ or if there are missing values (eg, no result [NR]) in a plasma concentration data series to be summarized.
 - For the calculation of summary statistics, BLQ values will be set to half the LLOQ
 - If an embedded BLQ value is considered anomalous within the concentration-time profile, this value will be excluded from the summary statistics.
 - Where there is NR, values will be set to missing.

- If there are fewer than 3 values in the data series, only the Min, Max and n will be presented. The other summary statistics will be denoted as not calculated (NC). BLQ is considered a value.
- If all the values are BLQ, then the arithmetic mean, arithmetic SD, median, Min and Max will be presented as zero, and the geometric mean and geometric CV% will be denoted as NC.
- If the value of the arithmetic mean or median is BLQ, it will be presented as zero, and the geometric mean and geometric CV% will be denoted as NC.

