9.6 Study Halting Criteria

General:

- Any SAE
- Three or more subjects within a cohort, with the same Grade 2 event ;
- Any single Grade 3 or above finding (with the exception of aPTT as explained below);
- Evidence of hematemesis or hematochezia in 2 or more subjects
- Any other findings that, at the discretion of the PI, indicate that the study should be halted;

Electrocardiograph (ECG):

Two or more subjects within a cohort who meet any of the criteria below:

- PR: >220 ms
- QRS: >120 ms
- QTcF > 450 ms for men and >470 ms for women; or
- Change from baseline (average of pre-dose triplicate ECGs): QTcF >60 ms.

Decisions are to be based on an average QTcF value of triplicate ECGs. If an ECG demonstrates a prolonged QT interval, 2 more ECGs should be obtained over a 10 minute period. The averaged QTcF values of the 3 ECGs will then be used for decision making.

Laboratory criteria:

- Two or more subjects within a cohort have a Grade 3 increase in aPTT (confirmed on repeat) as defined by the FDA toxicity grading scale as modified for this study and as appropriate for the administration of UV-4B ([Appendix II](#)).

If any of the above events occur, the study will be halted and the SMC will review the available safety data to determine if the study should proceed as planned. If none of the events described above have been observed, dose escalation will proceed according to the protocol requirements.

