10.7.6 Electrocardiogram

Triplicate 12-lead ECGs will be collected at predose on Day 1 only, and a single ECG will be collected at all other scheduled times. The mean of these 3 values (including any unscheduled values) at Day 1 predose will be used in all subsequent calculations of changes from baseline.

The ECG data will be obtained directly from the 12-lead ECG traces. These data include the QTc interval calculated using the Fridericia correction (QTcF), the PR and QT intervals, QRS duration, and heart rate. ECG data will be reviewed by the PI or designee to determine abnormal results and their clinical significance.

The ECG data will be summarized by treatment, together with changes from baseline.

An outlier analysis will be performed of all individual postdose measurements, including all repeat and unscheduled readings. The frequency of subjects with a maximum increase from baseline in QTcF interval will be summarized for each treatment according to the following categories: > 450 ms (male) or > 470 ms (female); > 500 ms; change from baseline > 30 ms to ≤ 60 ms; and change from baseline > 60 ms. Additionally, PR duration > 220 ms and QRS duration > 120 ms will be summarized.

Individual subject ECG data will be listed. Values for ECG parameters outside the clinical reference ranges will be flagged on the individual subject data listing. The reference ranges are 50-100 bpm for heart rate, 120-210 ms for PR interval, ≤ 120 ms for QRS duration, 340-450 ms for QT interval, > 450 ms for QTcF interval. All incidences of QTcF > 450 , > 480 , and > 500 ms will be flagged on the individual subject listing. All incidences of QTcF change from baseline > 30 and > 60 ms will be flagged on the individual subject listing.

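### Two SAP display rules are wrong as written: a concentration mean or median below the LLOQ is printed as zero, possibly under the printed minimum, and the QTcF reference range is inverted

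*SAP*

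**What the plan says.** **Concentration summaries (SAP 10.6.1).** The substitution rule is "For the calculation of summary statistics, BLQ values will be set to half the LLOQ". SAP 10.1 counts n, mean, SD, median, minimum and maximum as summary statistics for continuous data, so the substitution reaches all of them. Two display rules follow:

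- Every value BLQ: "If all the values are BLQ, then the arithmetic mean, arithmetic SD, median, Min and Max will be presented as zero". The geometric mean and CV% are not calculated.
- Mean or median BLQ: "If the value of the arithmetic mean or median is BLQ, it will be presented as zero". Again the geometric mean and CV% are not calculated. SD, minimum and maximum are not mentioned.

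Derivation of PK parameters has its own rule in SAP 10.5.2: "Concentration values that are below the level of quantification (BLQ) will be set to zero, with defined exceptions as follows". Those exceptions set embedded BLQ values, and BLQ values after the last quantifiable one, to missing.

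**ECG listing (SAP 10.7.6).** "Values for ECG parameters outside the clinical reference ranges will be flagged on the individual subject data listing". The ranges given include "340-450 ms for QT interval, > 450 ms for QTcF interval". The same section separately flags QTcF above 450, 480 and 500 ms on the listing, and its outlier summary uses above 450 ms for men and above 470 ms for women. Protocol 9.6 has the same two values as a halting criterion: "QTcF > 450 ms for men and >470 ms for women; or".

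**The concern.** For concentrations, the substitution rule and the mixed-series display rule work against each other. Once BLQ is replaced by LLOQ/2, no value in the series lies below LLOQ/2, and neither can a mean or median. Printing zero for those two statistics while the others stay as calculated gives a row that cannot describe any data set.

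For QTcF, every other range in the sentence describes the normal region (for example, a QRS of at most 120 ms). The QTcF entry describes the abnormal one. A programmer following the text would flag normal values as out of range and leave prolonged ones in range.

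Plasma concentrations and ECG changes are both secondary outcomes. PK data, and ECG listings and summaries, go to the Safety Monitoring Committee after each cohort (SAP 11). SAP 4 makes the SAP and its table shells the template for the study report.

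**Working it through.** **Concentrations.** Inputs: six active subjects per cohort (Protocol 11.2); BLQ = 0.5 in LLOQ units (SAP 10.6.1). The LLOQ is not stated, so everything is in multiples of it. The series are illustrative, since the plan gives no concentrations to reproduce.

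*Series A: 0.5, 0.5, 0.5, 0.5, 1.1, 1.3.*
- Mean = (4 × 0.5 + 1.1 + 1.3)/6 = 4.4/6 = 0.733.
- Median = 0.5; Min = 0.5; Max = 1.3.
- SD = √[(4 × 0.2333² + 0.3667² + 0.5667²)/5] = √(0.6733/5) = 0.367.
- Mean and median are both below 1, so the table prints 0 and 0, with SD 0.367 and Min 0.5.

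*Series B: 0.5, 0.5, 0.5, 1.2, 1.3, 1.4.*
- Mean = 5.4/6 = 0.900; median = (0.5 + 1.2)/2 = 0.85.
- Both are printed as 0 above a Min of 0.5, although half the subjects are quantifiable.

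*Series C: 0.5, 0.5, 0.5, 0.5, 3, 5.*
- Mean = 10/6 = 1.667 and is printed. The median of 0.5 is printed as 0, below the Min of 0.5.
- The geometric mean (0.989) is suppressed if a BLQ median alone triggers that clause.

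*All six BLQ.* Every statistic is printed as zero. The row agrees with itself but overrides the LLOQ/2 rule.

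*When is the mean overwritten?* With k of 6 values BLQ and m the average of the quantifiable values, the mean is below the LLOQ when 0.5k + (6 − k)m < 6, that is, m < (6 − 0.5k)/(6 − k):

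| k BLQ of 6 | mean overwritten if m is below (× LLOQ) |
|---|---|
| 1 | 5.5/5 = 1.1 |
| 2 | 5/4 = 1.25 |
| 3 | 4.5/3 = 1.5 |
| 4 | 4/2 = 2.0 |
| 5 | 3.5/1 = 3.5 |

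*Size of the error.* The overwritten statistic is at least LLOQ/2, by construction, and below the LLOQ, by the trigger. The printed zero is therefore too low by at least 0.5 and less than 1 LLOQ.

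**QTcF.** The two listing rules, applied literally:

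| QTcF (ms) | In stated range (above 450)? | Flagged as outside range? | Flagged by separate >450 rule? |
|---|---|---|---|
| 380, 400, 430, 450 | no | yes | no |
| 451, 481, 501 | yes | no | yes |

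The two flags are exact opposites, so every value carries one of them.

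**The case against.** On concentrations, showing an unquantifiable mean as zero is a presentation convention, and the all-BLQ rule does the same, so the zero looks deliberate. The error is bounded by one LLOQ, and the printed maximum still shows that drug was measured. All of this stands and keeps the point minor. It does not explain why mean and median follow one convention while minimum and SD follow another in the same row.

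On QTcF, the inverted sign is very probably a drafting slip. The separate flags and the outlier summary in the same section point the right way, and protocol 9.1.3 has the investigator or a designee review every ECG. That also stands: the output would be wrong and confusing, but prolonged values would not go unmarked.

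A reader might go further in three ways that the documents do not support:

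- **That trough or Day 10 means will appear as zero and suggest complete elimination between doses.** No LLOQ or expected concentration is visible, so nothing shows that these samples fall near the limit.
- **That 10.6.1 contradicts 10.5.2.** The latter governs parameter derivation, a different purpose, and it sets some BLQ values to missing rather than zero.
- **That omitting 470 ms for women from the listing flags is an error.** Protocol 9.6 sets halting criteria, not reference ranges. A 450 ms listing flag for both sexes is simply more sensitive, and the SAP outlier summary already uses 470 ms for women.

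**Conclusion.** Both rules give wrong output if programmed as written, and both are minor. In a mixed series the concentration table can print a mean or median below the printed minimum. This assumes that minimum and SD follow the LLOQ/2 substitution, as SAP 10.1 and 10.6.1 read together. The frequency cannot be estimated from the documents.

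The QTcF range is inverted rather than impossible, and it affects only one of two flags on a listing. PK parameters (10.5.2), dose proportionality, which is built on them (10.6.3), the QTcF outlier summary and the protocol 9.6 halting criteria do not use either rule.

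**What to change.** **10.6.1.** Apply one convention to every displayed statistic. The simplest is to keep LLOQ/2 throughout, delete the rule that overwrites a BLQ mean or median with zero, and print all-BLQ time points as BLQ (or on the same LLOQ/2 basis). Both display rules must change: if the all-BLQ rule stayed, such a time point would print 0 while five BLQ values with one of 1.5 would print (5 × 0.5 + 1.5)/6 = 0.667. Under LLOQ/2 throughout, series A prints mean 0.73, median 0.5, SD 0.37, Min 0.5 and geometric mean (0.5⁴ × 1.1 × 1.3)^(1/6) = 0.67. Zero throughout would also be coherent for arithmetic statistics, but the geometric mean would then need its own rule, because zeros cannot be logged.

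**10.7.6.** Change the QTcF reference range to at most 450 ms, which agrees with the existing listing flags. If the sex-specific 450/470 ms categories are preferred for the range, change the >450 ms listing flag to match; otherwise a woman at 460 ms would be both in range and flagged.

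**Cost.** A few lines of SAP text and the matching table and listing code. No new data are needed.

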10.6.2 Presentation of Pharmacokinetic Parameters

- For the calculation of summary statistics of PK parameters, all NR and NC values in a data series will be set to missing.
- The AUC values will be set to NC if they have been calculated using fewer than 3 concentrations, and/or 3 concentrations if the last is C_{max} .

10.6.3 Pharmacokinetic Statistical Methodology

All UV-4 plasma concentration data and derived PK parameters will be summarized by cohort.

If applicable, the PK parameters $AUC_{(0-8)}$, $AUC_{(0-last)}$, and C_{max} will be assessed for dose proportionality using the data from the last dose on Day 7.

To investigate the dose proportionality⁴ of AUCs and C_{max} , a statistical analysis using the power model⁴ will be conducted. The power model will have the form:

$$Y = a*(dose)^b$$

where Y is the PK parameter, and a and b are the coefficient and exponent, respectively, of the power equation.

By taking the natural logarithm (ln), the power model can be analyzed using linear regression and has the form:

$$\ln(Y) = \ln(a) + b*\ln(dose) + \text{error}$$

$$= \alpha + \beta*\ln(dose) + \text{error},$$

where α is the intercept, and β is the slope, and $\ln(dose)$ is based on the dose size for each subject. Estimates of slope and intercept along with their 90% confidence intervals will be reported. A minimum of 3 values per dose must be available for a given parameter to estimate dose proportionality using the power model.

For dose proportionality, the slope of the regression line (b) = 1 and for dose independence b = 0.

An additional classification term for treatment will be added to the above model to assess departure from linearity. Linearity, and hence the power model, will be assumed appropriate if the treatment term is not significant at the 5% significance level and the diagnostic plots seem reasonable. The assessment

of linearity may also be determined visually from plots by the Pharmacokineticist. This assessment may override the statistical assessment; where this occurs; it will be detailed in the CSR.

In previous single-dose escalation study⁵, it was concluded that UV-4 was dose proportional over the 30- to 1000-mg range in $AUC_{(0-inf)}$ where the 90% CI of the slope is (0.984, 1.043). The 90% CI of the slope for C_{max} was (1.048, 1.157), which was considered to be approximately dose-proportional. For the current study, if the assumption of linearity is considered acceptable and if the 90% CI for b is entirely with (0.8, 1.25), the relationship between dose and the PK parameter will be concluded to be dose proportional for the dose range studied. Caution should be used when interpreting results, since this study is not based on power calculations.

Scatter plots with regression lines will be presented with $\ln(\text{dose})$ as the x-axis versus the $\ln(\text{PK parameter})$ as the y-axis.

10.7 Safety and Tolerability Assessments

10.7.1 Drug Exposure and Compliance

Treatment exposure and compliance will be summarized descriptively by treatment group for the Safety population.

10.7.2 Adverse Events

A treatment-emergent adverse event (TEAE) is defined as an AE that occurs after administration of the first dose of study product or that is already present prior to the first dose of study product and becomes more severe postdose. In this study AEs will be evaluated from time of the first dose administration through the last follow-up visit. A medical condition that exists at the time of screening will be recorded as an AE only when it deteriorates at any time after the first study dose administration.

All AEs must be graded for severity and relationship to study product per Section 9.2.1 of the Protocol. AEs will be coded using the Medical Dictionary for Regulatory Activities (MedDRA[®]) AE coding system, version 19.0.

All TEAEs will be summarized for all subjects in the safety population by maximum severity, relationship to the study drug (as assessed by the Principal Investigator [PI]), and initial onset day. Serious TEAEs will be summarized by maximum severity, and relationship to the study drug. TEAEs leading to treatment discontinuation will also be summarized by maximum severity and relationship to the study drug. The frequency including the number of TEAEs, the number of subjects experiencing a TEAE, and the percentage of subjects experiencing a TEAE will also be summarized and displayed. TEAEs summaries will be presented by treatment, and by MedDRA (Version 19.0) system organ class and preferred term.

All AEs, severe AEs, serious AEs, deaths (if any), and events resulting in study discontinuation will be listed. Any individual dose-limiting toxicity (Protocol Section 9.7) will also be listed.

